7.2.3 Evaluation categories of patients

Patients not fulfilling the selection criteria of the trial ("non-eligible") will be excluded from the statistical analysis. Only casuistic reports will be provided for this group. All other patients will primarily be evaluated in an intent-to-treat analysis.

If a patient goes off treatment during the first two cycles for clearly other reasons than toxicity, he will not be included in the feasibility rate finding process and has to be replaced.

All patients having received at least one application of therapy are generally evaluable for toxicity.

7.2.4 Statistical methods

All parameters will be evaluated in an explorative or descriptive manner, providing means, medians, ranges, standard deviations and/or confidence intervals. If p values are calculated (e.g. in subgroup comparisons or across treatment arms), they will be presented explicitly without referring to hypotheses or a significance level. Usually, no error adjustment for multiple testing will be performed. Thus the p values will reflect the comparison-wise error and not the experiment-wise error. All p values will be two-sided if not stated otherwise. The statistical methods described in

Feasibility, toxicity, response and event rates at pre-specified time points are calculated, providing confidence intervals. In case of comparison between patient groups, these rates will be analyzed by Fisher's exact test, χ^2 test or Mantel-Haenszel test (or trend test according to COCHRAN/ARMITAGE), respectively.

Event related data like progression-free or overall survival will be estimated by the product limit method³⁶ (KAPLAN and MEIER, 1958) and compared using the logrank test. If the Peto logrank test³⁷ (PETO, 1972, 1977) is not appropriate because of violation of the proportional hazard assumption (HAYBITTLE 1988), Gehan's generalization of the Wilcoxon rank sum test for censored data (GEHAN 1965) will be applied, preferably in its modification by PETO (1972) and PRENTICE (1978). If appropriate, prognostic strata will be taken into account (PETO, 1977).

7.2.5 Interim and final analyses

As described and justified in 7.2.2, an interim analysis is performed, when 10 patients are evaluable for feasibility.

The main biometrical evaluation of the study and the compilation of the statistical report as part of the integrated clinical/biometrical report will be performed six months after termination of patient recruitment as well as after completion and/or correction of all case report forms. An additional analysis on long-term results will be performed 5 years later.

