7.2.2 Sample size calculation

The main objective of the trial is to assess, whether radiochemotherapy plus hyperthermia shows a promising feasibility profile in the treatment of locally recurrent rectal cancer. The primary endpoint is the feasibility rate as defined in section 7.2.1.

Conventional empirical phase I study designs in clinical oncology assume, that an antineoplastic treatment is not feasible, if an unacceptable toxicity occurs in more than 1 out of 3 or 4 patients; however, the occurrence of dose limiting toxicities (DLT) in 1/6 is accepted^{32,33,34,35}. This leads to the conclusion that the limit of acceptance is considered to be around 20% in medical cancer treatment.

In order to (from an ethical point-of-view) prevent to treat an unnecessarily high number of patients with a treatment regimen that is practically not feasible, a two-stage design according to SIMON (1989) will be applied. This allows for the termination of the study with a relatively low patient number in case of a definitely not acceptable feasibility rate. If this first step is passed without termination, further recruitment occurs in a second stage, in order to be able to ascertain a promising level of feasibility, hence qualifying the experimental treatment for further evaluation or application.

In summary, the trial design is based on the following assumptions:

- The experimental therapy would be rated as unacceptable, if the actual feasibility rate (= 1 withdrawal/DLT rate) was 70 % or lower.
- On the other hand, the multimodal regimen would be considered to be a promising candidate for further development (e.g. in a phase III trial), if the true feasibility rate amounted to 85% or more.
- Probability to accept the experimental therapy as well tolerable, in spite of a *true* feasibility rate of < 70% (i.e. withdrawal/DLT rate > 30%): 5% (type I error)
- Probability to reject the experimental therapy as not sufficiently feasible (<70%), although the *true* feasibility rate is promising (> 85%): 20% (type II error, corresponding to a power of 80%).

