According to these parameters, and using the variant out of the class of optimal twostage designs by SIMON (1989) that leads to the lowest expected number of patients required in case of true non-feasibility, $\mathbf{n} = 19$ patients evaluable for feasibility have to be recruited in the first stage. The combination will be rejected, if five or more of these patients fulfil the criterion of non-feasibility. In the second step, further patients will be recruited up to a total number of **59 evaluable cases**. The final conclusion of the trial will depend on the definite feasibility rate (and its confidence interval), the achieved level of treatment delivery (especially, the number of hyperthermia applications) as well as the complete information on type, frequency and severity of toxicities.

The precision of the estimation of the feasibility rate in the respective arms/strata is provided by confidence intervals in the following table, for different actual feasibility rate findings:

Feasibility rate	exact 90% confidence interval		
41/59 (≈70%)	58 79 %		
47/59 (80%)	69 88 %		
53/59 (90%)	81 95 %		

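### Section 7.2.5 places the interim analysis at 10 evaluable patients, but the two-stage design it cites in 7.2.2 places it at 19 and has no rule for 10

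*Protocol*

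**What the plan says.** Protocol section 7.2.2 adopts Simon's two-stage design. A regimen is unacceptable at a true feasibility rate of 70% or lower and promising "if the true feasibility rate amounted to 85% or more", with 5% type I error and 80% power. The variant chosen is the one "that leads to the lowest expected number of patients required in case of true non-feasibility". On that basis 19 "patients evaluable for feasibility have to be recruited in the first stage", and the rule attached to those 19 is: "The combination will be rejected, if five or more of these patients fulfil the criterion of non-feasibility". If the first stage is passed, recruitment continues to 59 evaluable patients. No acceptance count is given at 59; the conclusion is to rest on the feasibility rate and its confidence interval, the delivery of treatment and the toxicity picture.

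Protocol section 7.2.5 then says: "As described and justified in 7.2.2, an interim analysis is performed, when 10 patients are evaluable for feasibility". It gives no stopping boundary for 10 patients.

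**The concern.** The two sections give different triggers for the only numerical stopping rule in the protocol. Section 7.2.5 relies on 7.2.2 for its justification, and 7.2.2 neither mentions nor supports a look at 10. Someone running the trial from 7.2.5 would reach 10 patients with no rule to apply, because the five-failure count belongs to 19.

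Section 7.2.2 says the two-stage design is there to limit how many patients receive a regimen that turns out not to be feasible. The timing of the look and its boundary decide how well it does that, and they also enter the type I error and power.

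**Working it through.** **Inputs.** From 7.2.2: p0 = 0.70, p1 = 0.85, type I error at most 0.05, power at least 0.80, smallest expected size at p0; n1 = 19, stop at 5 or more non-feasible (14 or fewer feasible), n = 59. From 7.2.5: look at 10, no boundary. Assumption: the final cut-off, shown at 47/59 and 48/59.

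**Formulas.** Let X1 ~ Bin(n1, p) and X2 ~ Bin(n − n1, p) be the feasible patients in each stage. Stop early if X1 ≤ r1; accept if the total exceeds r.

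- Early stopping: PET(p) = P(X1 ≤ r1)
- Acceptance: A(p) = Σ P(X1 = x) · P(X2 ≥ r + 1 − x), for x = r1 + 1 to n1. Type I error is A(0.70); power is A(0.85).
- Expected size: n1 + (1 − PET) · (n − n1)

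**Step 1: reproduce the plan.** An exact search over two-stage designs returns r1/n1 = 14/19 and r/n = 46/59, that is, accept at 47 or more. This matches 19, five failures and 59. PET(0.70) = 0.7178, type I error = 0.0494, power = 0.8067, and expected size at 70% = 19 + (1 − 0.7178) × 40 = 30.3. The design in 7.2.2 is sound, so the 10 is the number out of line.

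**Step 2: a single look at 10 in place of the look at 19.** For the five-failure rule, expected size = 10 + (1 − 0.1503) × 49 = 51.6.

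| Look at | Stop if non-feasible | Accept at | Early stop at 70% | Expected N at 70% | Type I error | Power |
|---|---|---|---|---|---|---|
| 19 | ≥5 | 47/59 | 71.8% | 30.3 | 4.9% | 80.7% |
| 10 | ≥5 | 47/59 | 15.0% | 51.6 | 6.5% | 89.9% |
| 10 | ≥4 | 47/59 | 35.0% | 41.8 | 6.1% | 87.2% |
| 10 | ≥3 | 47/59 | 61.7% | 28.8 | 4.8% | 76.6% |
| 10 | ≥2 | 47/59 | 85.1% | 17.3 | 2.6% | 52.0% |
| 10 | ≥5 | 48/59 | 15.0% | 51.6 | 3.5% | 83.1% |
| 10 | ≥4 | 48/59 | 35.0% | 41.8 | 3.3% | 80.9% |
| 10 | ≥3 | 48/59 | 61.7% | 28.8 | 2.7% | 71.9% |
| 10 | ≥2 | 48/59 | 85.1% | 17.3 | 1.6% | 49.6% |

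With no early stop at all, type I error is 6.6% at 47/59 and 3.5% at 48/59. A look that can only stop for non-feasibility cannot exceed those values.

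**Step 3: a look at 10 added to the look at 19 (accept at 47/59).** Stopping at ≥5 of 10 leaves 4.9% and 80.7% unchanged, because five failures among the first 10 are already five among the 19. Stopping at ≥4 gives 4.8% and 79.9%; at ≥3, 4.2% and 72.9%.

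**The case against.** A reader might infer that following 7.2.5 breaks the 5% type I error, removes the early-stopping protection, or that the error rates can hold only with a look at 19. The documents do not support any of these.

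- The 6.5% needs three things the protocol does not say: that the look at 10 replaces the look at 19, that the five-failure count moves to 10, and that acceptance is at 47/59. The protocol's own table gives an exact 90% interval of 69 to 88% for 47/59, which does not exclude 70%. If the interval must lie above 70%, 48/59 is needed (lower limit 71.0%), and type I error is then at most 3.5% under any rule at 10.
- Stopping at 4 or 5 of 10 with acceptance at 48/59 meets both the 5% and the 80% targets.
- Section 7.2.5 does not repeal the rule in 7.2.2. If both looks are made, type I error does not rise, and with five failures as the boundary at 10 the chance of stopping early at 70% stays at 71.8%.
- Section 5.9 also lets the sponsor end the trial for severe or frequent adverse events, though at discretion and without a threshold.

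All of this stands, and it limits the consequences that can be claimed. It does not remove the contradiction or supply the missing boundary. The combinations that meet both error targets with a single look at 10 do so by giving up most of the early stopping: 15.0% or 35.0%, against 71.8%.

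**Conclusion.** The protocol contradicts itself on when its interim analysis takes place. The inputs in 7.2.2 reproduce 19 and 59 exactly, so 10 is the wrong figure and 7.2.5 cites a justification that does not exist.

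The planned operating characteristics are not assured if 7.2.5 is followed in place of 7.2.2. At every boundary tabulated and both final cut-offs, a look at 10 that replaces the look at 19 either misses the 5%/80% targets or lowers early stopping at 70% feasibility to about 35% or less. With the five-failure count carried over, the expected number treated at 70% rises by 51.6 − 30.3 = 21.3 patients. That figure depends on this one scenario but not on the final cut-off. The type I error does depend on the cut-off (6.5% at 47/59, 3.5% at 48/59), which the protocol leaves unstated, so an inflated error rate is possible but not established.

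This is an internal inconsistency, not a flaw in the chosen design. It should be corrected because it governs the stop-or-continue decision.

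**What to change.** In 7.2.5, replace 10 by 19 and repeat the rule from 7.2.2: the regimen is rejected if five or more of the 19 are non-feasible. If an additional look at 10 is intended, 7.2.2 should state its boundary, say that the look at 19 remains, and give the recomputed type I error and power. Those figures need a stated final cut-off.

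The correction is one sentence and adds no patients or procedures.

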8 STUDY DOCUMENTATION AND ARCHIVING

8.1 DOCUMENTATION AND INFORMATION FLOW

All patient-related data are recorded in a pseudonomized way. Each patient is unequivocally identified by a trial subject number, attributed at recruitment into the study. The investigator has to keep a patient identification log, including the full name and address of the subject and eventually additional relevant personal data such as hospital record number, home physician etc. In addition, patients who were screened in order to be entered into the study, but who could not be recruited for whatever reason (informed consent not given, not fulfilling selection criteria etc.) are recorded in a "patient reject log". All the data retrieved during the conduct of the study are entered into the appropriate case record forms (CRF, appendix 8) by the investigator or another person authorized by the investigator (co-investigator). The CRFs are provided by the study secretariat and are explained to the investigator by the study monitor.

All recorded data have to be plausible and complete. Please respect the following technical details when using the CRFs:

- Use black or blue ballpoint pens only in order to insure that all copies are legible.
- Write only one letter or numeral into each of the open boxes of the respective data fields. Closed boxes have to be crossed only (check boxes).
- All data fields have to be filled, except for those referring to open questions. If a specific test was not performed or an information item is definitely not available or applicable, information on this should be provided (not done= ND, not applicable, not available = NA, unknown= UK).
- If a date is not known exactly, please fill in the respective field according to the following example: 08 05.
- If any corrections have to be performed in the CRF by the investigator or coinvestigator, they have to be performed according to GCP principles, i.e. the original entry has to be crossed out but remain legible.
- The correct version is then written legibly beside or above the original one.
- The correction (or addition) has to be dated and signed or initialled.

1	2	1	3	0	3
day		month		year	

Version to be corrected:

			2 date, initials				
1	2	1	ŝ	0	3		

corrected version:

•		•	•	•)
da	у	mo	nth	ye	ar

- Please write legibly and use printing letters

The investigator is obliged to complete the case report forms within a reasonable time period after retrieval of the data (i.e. usually within 2 weeks). The completed forms are signed by the investigator, where necessary. The original has to be sent to the data management office or handed over to the monitor in case of on-site visits. A copy remains with the investigator. The study office or monitor checks the forms for completeness and plausibility. In case of queries, the form or a photocopy of it will be sent or given back to the investigator for clarification/correction/ completion. Queries have to be handled within 4 weeks.

After finalisation of the data checks by the study office/monitor the originals or fair copies are sent to the biostatistical center. If additional queries arise there during computer data entry, they are handled by the investigator via monitor or study office contacts.

8.2 DATA ARCHIVING

The original forms of all relevant study documents including CRFs are stored at the office of the coordinating investigator/sponsor for at least 10 years after completion of the final study report. The investigators have to archive major administrative documents (correspondence with ethical committee, authorities, sponsor etc.), the patient identification log, the signed informed consent forms, and the main study documents (protocol, amendments) for the same time period. The original patient records have to be archived according to the standard procedures of the respective institution, but at least for 10 years.

9 FINANCING

The sponsor/coordinating investigator(s) will take care of the financing/funding of the study. The "Deutsche Krebshilfe" is the main funding source.

10 USE OF INFORMATION AND PUBLICATION

Any documents supplied in connection with this study, and not previously published, are considered confidential information. This information includes the clinical protocol, workbooks if applicable, case report forms etc. This confidential information, shall not be disclosed to others without prior written consent from the coordinating investigator and shall not be used except in the performance of this study.

The information developed during the conduct of this clinical study is also considered confidential. To allow for the use of the information derived from this clinical study and to insure compliance to current regulations, the investigator is obliged to provide the coordinating investigator with complete test results and all data developed in this study.

The authorship list will be agreed by all investigators prior to publication. The study will only be published once it is completed with respect to the primary endpoint and

the corresponding analysis has been performed by the coordinating investigator or his delegate.

11 ETHICAL AND LEGAL REQUIREMENTS

11.1 GENERAL REQUIREMENTS AND AGREEMENTS

The study will be performed according to current legal standards. The ICH E6 Harmonised Tripartite Guideline for Good Clinical Practice, dating from 1997, will be taken into account. In Germany, the requirements according to the following documents will be fulfilled: Deutsches Arzneimittelgesetz (AMG, 12. Novelle, 2004), "Grundsätze für die ordnungsgemäße Durchführung der klinischen Prüfung von Arzneimitteln" (Bundesanzeiger Nr. 243 vom 30.12.1987) and "Verordnung über die Anwendung der Guten Klinischen Praxis bei der Durchführung von klinischen Prüfungen mit Arzneimitteln zur Anwendung am Menschen" from 9th August 2004. The coordinating investigator has at least two years of experience in clinical trials on medicinal products. He is at the same time sponsor of the study with respect to GCP regulations (according to article 7 of the EC Commission Directive 2005/28/EC), since the trial at hand is a non-commercial or investigator-initiated clinical trial. The sponsor is responsible for the trial master file according to chapter 4 of the EC Directive 2005/28/EC. The sponsor may delegate this function (or other requirements mentioned in the following sections) to another individual, a company, an institution or an organization.

11.2 DECLARATION OF HELSINKI

The trial will be performed in accordance with the Declaration of Helsinki, as decided upon by the 18th World Medical Assembly, Helsinki, Finland, June 1964 (amended by subsequent World Medical Assemblies in Tokyo, Japan, October 1975, Venice, Italy, October 1983, Hong Kong, September 1989, Somerset West, South Africa, October 1996, and Edinburgh, Scotland, 2000. The declaration is included as appendix 7.

11.3 INFORMED CONSENT OF THE PATIENT

Before recruitment into the clinical trial each patient will be informed, that participation in the study is completely voluntary, and that he or she may withdraw the participation in the trial at any time without any declaration of reasons. This will

not lead to any disadvantage for the respective patient. If the withdrawal is caused by any adverse drug events, the patient should inform the investigator about this fact.

The treating physician will inform the patient about the drugs to be used and their possible adverse effects. At the same time he/she will be informed on the nature and objectives of the study, expected advantages of the participation, possible hazards of the study and alternatives of treatment. The patient will also receive the necessary information on the trial specific insurance and his obligations with this respect. The patient will have sufficient time for his decision and opportunity to ask additional questions. Moreover, the patient will receive a written "patient information" (Appendix 4), containing all relevant information for the patient's decision and the course of the study.

The consent of the patient to participate must be obtained in writing before recruitment into the study. The informed consent form (Appendix 5) must be dated and signed by the patient. Thereby, he declares his voluntary consent to participate in the study and his willingness to comply with the requirements of the trial and the instructions of the treating investigator during the course of the study.

There are two copies of the informed consent form: one for the patient and one to be kept by the investigator in his study documents. The informed consent is only valid after receiving the patient's signature. Thereafter, the patient can be entered into the study if he/she fulfils the selection criteria.

With the declaration of consent the patient agrees that data on his disease are recorded within the framework of the clinical trial and that they are transferred to the sponsor in an pseudonymized way. Moreover, the patient agrees that delegates from the responsible authorities or the sponsor may have direct access to his/her original medical records for trial related monitoring, audit, review and regulatory inspection.

11.4 QUALITY ASSURANCE

11.4.1 Standardisation

The evaluation criteria are similar for all participating centers. Each center has to report its normal ranges for haematology and blood chemistry to the coordinating investigator. The respective laboratory institutions have to participate in an appropriate quality assurance program. Toxicity is recorded in a standardized way according to the NCI CTC criteria for categorization and grading. Evaluation of response efficacy is performed according to RECIST standards.

11.4.2 Monitoring / source data verification

The study will be monitored externally by regular site visits and telephone calls to the investigator by authorized personnel of the principal investigator. Queries or monitoring visits may take place before, during and after recruitment of patients into the study. The number of contacts will depend on the characteristics of the respective center, e.g. the number of recruited patients. According to the investigator's agreement, the monitor is allowed to access the trial documentation and the patients' personal medical records in the participating center.

In order to assure the quality of the data, all entries into the CRFs are formally inspected for completeness and plausibility. During site visits, an additional control with respect to identity of the data recorded in the personal patient records and in the CRF (Source Data Verification) may be performed. In addition, the monitor should review original patient records, drug accountability records and document retention (study file). Additionally, the monitor should observe study procedures and will discuss any problems with the investigator.

11.4.3 Audits

In case of an audit by the sponsor or an appropriate authority the investigator will make available all relevant documents. If an audit visit by a regional authority is announced, the respective center should inform the sponsor/coordinating investigator as early as possible in order to allow for an appropriate preparation and support. The inspected investigator or organisational institution of the study will be informed on the result of the audit.

